7.3.4 Randomization and masking

The recruited patients of each hospital will be **randomly divided in two groups**, through an electronic randomization statistical software that will generate a specific identification patient number for the study and will perform a randomization of the patients. The ratio will be 1:1.

Given the nature of the study, it will be a **single blinded trial**, since the newborns do not know which of the two protocols is applied to them.

7.4 Variables and measurements

Independent variable

The independent variable is the **invasive mechanical ventilation protocol** used during the weaning. It is conceived as a **dichotomous qualitative nominal variable** and is expressed as PSV/ACVGV:

- PSV: Pressure support ventilation
- ACVGV: Assist control volume guarantee ventilation

Dependent variables

There are two dependent variables: **number of reintubations** and **time of weaning**.

The **number of reintubations** is the main dependent variable. It is a **discrete quantitative variable**. The higher the number of reintubations, the higher the risk of complications, so it is a good variable to determine which protocol is more effective. Extubation failure is defined as reintubation within 24-72 hours, so the number of reintubations will be counted for the first 72 hours after the extubation.

The **time of weaning** is the secondary dependent variable. It is a **continuous quantitative variable**. It is counted from the moment the weaning is started until the extubation is executed. The longer this time is, the greater the risk of complications arising from invasive ventilation that the child may have, so it is a good variable to determine which protocol is more effective.

Covariates

- **Gestational age at birth/type of preterm:** once is born, the baby will be classified into one of these categories. It is a *dichotomous qualitative ordinal variable*:
 - Extremely preterm (< 28 weeks of gestation)
 - Very preterm (28-32 weeks of gestation)
- **Birthweight:** it is a *continuous quantitative variable* measured in grams.
- **Sex:** it is a *dichotomous qualitative nominal variable*. Categorized as men or women.
- **CPR after birth:** it is a *dichotomous qualitative nominal variable*. It will be expressed as yes or no.

- **5-minute Apgar score** (see Annex 1): It is a quantitative variable, but categorized in the following intervals, resulting in a *polychotomous qualitative ordinal variable*:
 - Apgar 0-3
 - Apgar 4-6
 - Apgar 7-10
- **Risk factors of prematurity:**
 - **Previous preterm birth:** it is a *dichotomous qualitative nominal variable*. It will be expressed as yes or no.
 - **Second trimester miscarriage (> 16 weeks):** it is a *dichotomous qualitative nominal variable*. It will be expressed as yes or no.
 - **Multiple pregnancy:** it is a *dichotomous qualitative nominal variable*. It will be expressed as yes or no.
 - **Chorioamnionitis:** it is a *dichotomous qualitative nominal variable*. It will be expressed as yes or no.
 - **Premature rupture of membranes** it is a *dichotomous qualitative nominal variable*. It will be expressed as yes or no.
 - **Maternal age:** it is a *continuous quantitative variable*. Measured in years
 - **Maternal size:** it is a *continuous quantitative variable*. Measured in cm.
 - **Cervical surgery:** it is a *dichotomous qualitative nominal variable*. It will be expressed as yes or no.
 - **Congenital uterine anomaly:** it is a *dichotomous qualitative nominal variable*. It will be expressed as yes or no.
 - **Diabetes or gestational diabetes:** it is a *dichotomous qualitative nominal variable*. It will be expressed as yes or no.
 - **Sexually transmitted infection:** it is a *dichotomous qualitative nominal variable*. It will be expressed as yes or no.

- **Smoking during pregnancy:** it is a *dichotomous qualitative nominal variable*. It will be expressed as yes or no.
- **Consuming alcohol or other toxics during pregnancy:** it is a *dichotomous qualitative nominal variable*. It will be expressed as yes or no.
- **Short intragestational period:** it is a *dichotomous qualitative nominal variable*. It will be expressed as yes or no.
- **Extrauterine infection:** it is a *dichotomous qualitative nominal variable*. It will be expressed as yes or no.

All these covariates will be obtained from the clinical history of the mother and the newborn, as all these information will be obtained before the recruitment of the patient in the study. Special importance will be given to the gynaecological clinical history of the pregnancy.

Table 4 - Summary table of variable

	Variable	Type of data	Categories or values
Independent variable	Protocol of invasive mechanical ventilation	Dichotomous qualitative nominal	PSV / ACVGV
Dependent variables	Number of reintubations	Discrete quantitative	Numerical
	Time of weaning	Continuous quantitative	Numerical (days)
Covariates	Sex	Dichotomous qualitative nominal	Men / Women
	Type of preterm	Dichotomous qualitative ordinal	Extremely preterm / Very preterm
	Birthweight	Continuous quantitative	Numerical (grams)
	CPR after birth	Dichotomous qualitative nominal	Yes / No
	5-minute Apgar score	Polychotomous qualitative ordinal	0-3 / 4-6 / 7-10
	Risk factors of prematurity		
	Previous preterm birth	Dichotomous qualitative nominal	Yes / No
	Second trimester miscarriage	Dichotomous qualitative nominal	Yes / No

	Multiple pregnancy	Dichotomous qualitative nominal	Yes / No
	Chorioamnionitis	Dichotomous qualitative nominal	Yes / No
	Premature rupture of membranes	Dichotomous qualitative nominal	Yes / No
	Maternal age	Continuous quantitative	Numerical (years)
	Maternal size	Continuous quantitative	Numerical (cm)
	Cervical surgery	Dichotomous qualitative nominal	Yes / No
	Congenital uterine anomaly	Dichotomous qualitative nominal	Yes / No
	Diabetes or gestational diabetes	Dichotomous qualitative nominal	Yes / No
	Sexually transmitted infection	Dichotomous qualitative nominal	Yes / No
	Smoking	Dichotomous qualitative nominal	Yes / No
	Consuming alcohol or other toxics	Dichotomous qualitative nominal	Yes / No
	Short intragestational period	Dichotomous qualitative nominal	Yes / No
	Extrauterine infection	Dichotomous qualitative nominal	Yes / No

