3.3.3. Invasive mechanical ventilation

There are a lot of different modalities of invasive mechanical ventilation.

Only the two modalities related to this project will be discussed: **assist-control volume guarantee ventilation** and **pressure-support ventilation**.

Assist-control ventilation

Assist-control volume guarantee ventilation (ACVGV) is a combination mode of ventilation in which the **current tidal volume is delivered in response to the inspiratory effort or if no patient effort occurs within a set period of time**. The period is determined by the backup respiratory rate set on the ventilator. When there is an inspiratory effort from the patient, the ventilator senses this as a trigger and initiates another controlled breath.

All breaths are done by the ventilator, the patient cannot take spontaneous breaths. (53)

The advantage of ACV (assist-control ventilation) is that it significantly reduces work of breathing and decreases myocardial oxygen demand. The disadvantages of ACV in the active patient are that it is less comfortable than spontaneous breathing and that it can induce respiratory alkalosis and breath-stacking.

With volume ACV, the volume is set by the professional, so it is constant, but the airway pressure varies. When patients with severe hypoxaemia require high PEEP and FiO₂ settings to maintain adequate oxygenation, the airway pressures that are generated to deliver the desired tidal volume increase. This increasing pressure can be measured as the peak inspiratory pressure or the plateau pressure, all of which attempt to describe the pressures that are transmitted through the airways at different levels and at different points in the respiratory cycle. (49)

[figure not shown]

Figure 12 - Assist-control ventilation curves (54)

Pressure support ventilation

Pressure support ventilation (PSV) is used in patients who are awake enough to breathe spontaneously. It augments the patient's spontaneous inspiratory efforts with the selected level of positive airway pressure. (49) The ventilator does not do any of the breathing, the patient starts all the breaths, and the ventilator helps with each one with a certain pressure. The **beginning and end of the breaths are therefore determined by the patient's effort.** (53)

Inspiratory pressure is delivered until the flow decreases to a predetermined level (usually 25% of peak flow). PSV allows the clinician to control the desired pressure support, PEEP, and FIO₂.

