7.8 Safety

The intervention carried out in this study does not entail any added risk to the patient, as all patients on invasive mechanical ventilation require the weaning process prior to extubation.

In this study, the intervention focuses only on the assignment of the weaning protocol. The two protocols used in the trial are those currently used in NICUs, with studies that support their use.

So, patients on the study will not have any additional risk compared to patients in the same situation outside the study.

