8.1. Descriptive analysis

First, we will summarize all dependent, independent variables and covariates.

- **Qualitative variables** (protocol used, type of preterm, CRP after birth, 5-minute Apgar score and most covariates related with risk factors) will be described using **proportions**.
- **Quantitative variables** (number of reintubations, time of weaning, birthweight, maternal age, and maternal size) will be summarized by **means, standard deviation, medians, and interquartile range (IQR)**

The dependent variables are quantitative, so a comparison of medians will be made in relation to the assigned protocol, PSV or ACVGV, will be done. These descriptives will be stratified by the categories of the covariates.

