8.2 Bivariate interference

Both dependent variables, number of reintubations and time of weaning, are quantitative. The relation between number of reintubations and each protocol, will be contrasted using **T-Student test**. The relation between time of weaning and each protocol will be contrasted using **Kaplan-Meier**, as it is a survival analysis.

The relation between **quantitative covariates** and each protocol, will also be contrasted using **T-Student test**.

And the relation between **qualitative covariates** and each protocol will be contrasted by **Xi-squared test** or **Fisher's exact test** (if the expected number of cases in a cell will be less than 5).

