8.3 Multivariate interference

It will be necessary to do a multivariate analysis adjusting the covariates according to the independent variable with the dependent variables that can interfere in the results, to avoid possible confusion.

Poisson regression model will be used for the association between the intervention and the number of reintubations, which is a **discrete quantitative variable**.

Cox regression models will be used for the association of the intervention with the **time** of weaning, which is a **continuous quantitative variable**. It is calculated as a survival analysis.

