Annex 7 – Data form

ETIQUETA
IDENTIFICATIVA

DATA FORM

En relació amb el pacient

Setmanes de gestació	
Tipo de preterme	
Per al néixer	
Sexe	
CPR després de néixer	
Apgar score als 5 minuts	

En relació amb la mare

Part preterme previ	
Avortament del segon trimestre	
Edat	
Alçada	
Cirurgia cervical prèvia	
Anomalia uterina congènita	
Diabetis pregestacional	
Malaltia de transmissió sexual	
Fumadora	
Consum alcohol o altres tòxics	
Període intragestacional curt	
Infecció extrauterina	

En relació amb l'embaràs

Embaràs múltiple	
Corioamnionitis	
Ruptura prematura de membranes	
Diabetis gestacional	

En relació amb la intervenció

Codi del protocol utilitzat	
Reintubació	
Temps de weaning (en dies)

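### The plan does not settle whether infants are analysed by the weaning mode allocated or the mode used; read literally, section 7.4 and the data form give an as-treated comparison that could be biased if infants change mode.

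*Combined protocol and SAP*

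**What the plan says.** The wording differs from place to place.

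- **Section 7.4:** "The independent variable is the invasive mechanical ventilation protocol used during the weaning". The variable has two values, PSV or ACVGV.
- **Annex 7:** the intervention block has one treatment item, "Codi del protocol utilitzat" (code of the protocol used). There is no item for the allocated arm or for a change of mode.
- **Section 8.1:** "so a comparison of medians will be made in relation to the assigned protocol, PSV or ACVGV".
- **Section 8.2 (primary test):** "The relation between number of reintubations and each protocol, will be contrasted using T-Student test".
- **Section 8.3 (adjusted model):** "Poisson regression model will be used for the association between the intervention and the number of reintubations".
- **Section 7.8:** "In this study, the intervention focuses only on the assignment of the weaning protocol".

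No section names an intention-to-treat or per-protocol population, mentions a change of mode, or says how an infant weaned on both modes is classified. The only withdrawal criteria in section 7.2 are revoked consent and death, so an infant who changed mode would stay in the data.

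**The concern.** Randomisation protects the comparison only if infants are grouped as randomised. Section 12.1 relies on this when it says that no differences between the groups are expected. If the statistician groups infants by the mode used, as section 7.4 and the form literally direct, any infant who changes mode can change group, and the reason for the change may be related to the risk of reintubation.

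A change of mode is plausible in this trial. Of PSV, section 3.3.3 says "The ventilator does not do any of the breathing, the patient starts all the breaths", whereas ACVGV delivers a breath if no effort occurs within a set time. Section 10.3 says the process can take days or weeks, and the treating team is not masked. Frequent apnoea is itself among the reintubation criteria in section 7.5, so infants moved for weak respiratory drive could well be at higher risk. Both outcomes are exposed, since the same grouping variable serves reintubation and time of weaning.

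**Working it through.** **1. The plan's own figure.** Section 7.3.1 gives alpha 0.05 two-sided, beta 0.2, a proportion of 16% in one group, a difference printed as 0.1 percent units, and 5% drop-out. Read as 16% against 26%, with unpooled variance:

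n = (1.960 + 0.842)² × (0.16×0.84 + 0.26×0.74) / 0.10² = 7.849 × 0.3268 / 0.01 = 256.5, so 257; then 257 / 0.95 = 270.5, so 271.

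This matches the stated 271 per group. The 257 evaluable infants per arm are used below.

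**2. Set-up of the illustration.** There is no true effect and each randomised arm has 16% risk. A share *s* of the PSV arm, with reintubation risk *r*, moves to ACVGV and is coded as ACVGV. Both *s* and *r* are assumptions, because the documents give neither. Grouped by mode used:

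- PSV group: size 257(1 − s), risk (0.16 − s·r)/(1 − s)
- ACVGV group: size 257(1 + s), risk (0.16 + s·r)/(1 + s)

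Example, s = 0.10 and r = 0.32: PSV has (0.16 − 0.032)/0.90 = 14.2% of 231, and ACVGV has (0.16 + 0.032)/1.10 = 17.5% of 283. The difference is 3.2 points before rounding. The chance of significance is from a two-sided pooled z test of two proportions. The plan's t test on counts is not modelled.

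| s | r | PSV as used | ACVGV as used | Apparent PSV benefit (points) | Significant, either direction |
|---|---|---|---|---|---|
| 5% | 30% | 15.3% | 16.7% | 1.4 | 7.1% |
| 10% | 32% | 14.2% | 17.5% | 3.2 | 16.6% |
| 10% | 40% | 13.3% | 18.2% | 4.8 | 31.8% |
| 10% | 16% | 16.0% | 16.0% | 0 | 5.0% |
| 10% | 10% | 16.7% | 15.5% | −1.2 | 6.7% |

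By allocated arm, the difference is 0 and the error rate is about 5% in every row.

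**3. Switching in both directions.** If 10% of each arm, at 32% risk, changes to the other mode, each as-used group has risk 0.90 × 0.1422 + 0.10 × 0.32 = 16.0%, and the bias cancels.

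**4. What the table shows.** The sign and size depend on who changes mode and in which direction. With *s* from 5 to 20% and *r* from 24 to 48%, all out of PSV, the apparent PSV benefit runs from 0.8 to 13.3 points. Time of weaning was not quantified.

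**The case against.** The best reply is that *used* is simply this protocol's word for the allocated arm. Section 7.5 randomises the infant and then describes each group by the protocol that will be used. Section 7.7 has the randomised allocation tell the neonatologist which protocol to use. Sections 7.8 and 8.1 speak of assignment, and the form asks for a code, which could be a masked arm code. On that reading there is no conflict. This has real force, and it is why the finding is an ambiguity and not a declared as-treated analysis. But it leaves the definition in 7.4 and the wording of the form as they stand, and neither 8.2 nor 8.3 resolves them.

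Three stronger conclusions are tempting, and the documents do not support them.

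- *That infants moved out of PSV will be counted as ACVGV.* No section mentions switching or its coding. An infant weaned on both modes has used both.
- *That switching is one-sided, so the bias favours the hypothesis.* Section 3.3.3 also lists drawbacks of assist-control in the active patient (discomfort, alkalosis, breath-stacking) that could prompt moves the other way. It also makes spontaneous breathing a condition for starting weaning, although the starting criteria in 7.5 do not list it; those passages should be reconciled.
- *That the loss cannot be repaired.* Software performs the randomisation (7.3.4) and the biostatistician prepares the allocation (7.7), so the arm could be recovered and linked by patient number.

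What remains is that no section says the allocation is merged into the analysis database, and the form has no place for the date or reason of a change of mode.

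**Conclusion.** The point holds as an unresolved contradiction with a possible bias. The definition in 7.4 and the only treatment item on the form refer to the mode used, 8.1 and 7.8 refer to assignment, and the primary test and models are silent. Taken literally, the comparison is not randomised once any infant changes mode.

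The size cannot be fixed from the documents. Under the assumptions shown, the spurious PSV advantage is 1.4 points for 5% switching at 30% risk and 4.8 points for 10% at 40%, with about 7% and 32% of null trials significant. These figures require all switching to run out of PSV, above-average risk in the switchers, and coding as ACVGV. With average-risk switchers, or equal high-risk switching both ways, the bias is zero; with lower-risk switchers it favours ACVGV. The figures show what the wording permits, and they do not forecast what will happen.

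The matter should still be settled before the first infant is randomised. It governs the grouping for both outcomes, and details of a change of mode are difficult to recover later.

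**What to change.** 1. **Section 7.4:** define the independent variable as the protocol allocated at randomisation.
2. **Section 8:** state that all randomised infants are analysed by allocated arm, for reintubations and for time of weaning, and use that term throughout 8.1 to 8.3.
3. **Annex 7:** replace the single code with the allocated-arm code (taken from the randomisation record and masked to the analyst), the mode in use at extubation, and the date, time and reason of any change of mode.
4. Keep grouping by mode used only for a labelled sensitivity analysis.

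The cost is one definition, one sentence and a few form fields. The planned 271 per group is unchanged. The drawback is that changes of mode may dilute the estimated difference between the arms. No clinical rule for changing mode is proposed here; the documents give none.

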7.3 Sampling

7.3.1 Sample size

We estimated the sample size using the free online software GRANMO, and the setting for two independent proportions.

In the view of the literature published so far, the proportion of reintubation in preterm newborns that are on invasive mechanical ventilation is 16% (studies differ between 12% and 20%, an average has been made).(62,63)

Accepting an alpha risk of 0.05 and a beta risk of 0.2 in a two-sided test, **271** subjects are necessary in first group and **271** in the second to recognize as statistically significant a difference greater than or equal to 0.1 percent units. A proportion in one of both groups has been estimated to be 16%. It has been anticipated a drop-out rate of 5% (0,05).

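### Gestational age is collected in weeks but defined for analysis only as two classes split at 28 weeks; entering the weeks in both adjusted models is a small, free gain in precision

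*Combined protocol and SAP*

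**What the plan says.** Section 7.4 treats gestational age at birth and type of preterm as a single covariate and makes it dichotomous: "once is born, the baby will be classified into one of these categories". The cut is at 28 weeks. Table 4 has no row for weeks; its only entry for the variable is type of preterm, with values "Extremely preterm / Very preterm". Section 8.1 lists type of preterm among the qualitative variables and does not list weeks among the quantitative ones. It also says that the descriptive tables will be stratified by the covariate categories.

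Annex 7 nevertheless collects "Setmanes de gestació" (weeks of gestation) in a field separate from type of preterm.

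Section 8.3 plans a Poisson model for the number of reintubations and a Cox model for weaning time. Both are adjusted for covariates, but none is named. Birthweight is a separate, continuous covariate in 7.4.

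**The concern.** The protocol describes a gradient with gestational age. Section 3.1.5 says that adverse outcomes become less likely as it rises, and section 3.2.2 says that NRDS becomes more frequent and more severe as it falls. A two-level term replaces the gradient with one step at 28 weeks, so infants several weeks apart within a class are treated alike.

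Section 7.3.4 describes randomisation within hospital and does not name gestational age as a stratification factor. Section 12.1 relies on the multivariable analysis to deal with confounding factors. A binary term cannot adjust for chance imbalance within a class, except through correlated variables such as birthweight. At stake is some precision in the adjusted estimates. The finer value is already on the form, and no reason is given for using the split in a model.

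**Working it through.** **1. The plan's own figure.** Section 7.3.1 gives two-sided alpha 0.05, beta 0.2, a reference proportion of 16%, a "difference greater than or equal to 0.1 percent units" (read as 10 percentage points) and 5% drop-out. With 16% against 26% and unpooled variance:

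n = (1.960 + 0.842)² × (0.16×0.84 + 0.26×0.74) / 0.10² = 256.5, rounded up to 257; 257/0.95 = 270.5, rounded up to 271 per arm.

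This matches the plan. The formula has no covariates, so the coding of gestational age cannot change N.

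**2. Share below 28 weeks (p).** Section 7.3.3 uses NRDS incidences of 70% and 50%, averaged to 55%.
- Births under 32 weeks: 0.70p + 0.50(1−p) = 0.55 gives p = 0.25. The 5% and 15% in section 3.1 agree: 5/20 = 0.25.
- Infants with NRDS: 0.25 × 0.70/0.55 = 0.32.
- Ventilated infants: 0.32 × 0.50/0.40 = 0.40. This uses the 40% from 7.3.3 and assumes that the half quoted in 3.3.3 for infants under 28 weeks applies to those with NRDS.

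**3. Variance of weeks lost by the split.** The documents do not give the distribution of weeks, so it is assumed and varied. The loss is 1 − r² between weeks and the indicator for under 28 weeks. For normal weeks it is 1 − φ(z_p)²/[p(1−p)]; for uniform weeks it is 1 − 3p(1−p).

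| p | Normal | Uniform |
|---|---|---|
| 0.25 | 46% | 44% |
| 0.32 | 41% | 35% |
| 0.40 | 38% | 28% |
| 0.50 | 36% | 25% |

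Four discrete shapes over completed weeks 23-31 give 25-34%. The overall range is 25-46%.

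**4. With continuous birthweight also in the model.** For normal weeks, p from 0.25 to 0.50 and an assumed correlation of 0.6-0.9 between weeks and birthweight, 14-37% of the variance of weeks is still not captured by the split and birthweight together.

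**5. Effect on the reintubation estimate.** Simulated adjusted Poisson model with robust standard errors, 1,000 trials per row. Inputs: 514 evaluable infants (542 × 0.95, rounded down), 16% against 26%, reintubation as yes/no, 40% under 28 weeks, correlation with birthweight 0.75, birthweight in both models.

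| Assumed rate ratio per SD of weeks | Power, split | Power, weeks | SE, split | SE, weeks | Fall in SE |
|---|---|---|---|---|---|
| 1.5 | 79.4% | 79.7% | 0.1764 | 0.1754 | 0.6% |
| 2.0 | 79.7% | 81.3% | 0.1717 | 0.1684 | 1.9% |

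Each power has a Monte Carlo standard error of about 1.3 points, so the gain is small and not sharply measured.

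**6. Effect on weaning time.** Simulated Cox model: 514 infants, no censoring, true log hazard ratio 0.25, birthweight correlation 0.8. The standard error of the treatment term hardly changes. With the split, the adjusted log hazard ratio is pulled towards zero. Entering weeks raises the squared test statistic by about 4% if weeks and weaning time correlate at 0.3, and by up to about 28% if they correlate at 0.6. The documents give no value for that correlation.

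**The case against.** The strongest reply is that the effect on the primary outcome is negligible and that every size depends on assumptions. This largely stands. The distribution of weeks, its correlation with birthweight and its prognostic strength are not in the documents. Where section 3.3.3 lists what helps to predict successful extubation, it names infant size among other factors but not gestational age, and size is already represented by continuous birthweight. Allocation is randomised, so any imbalance within a class is due to chance.

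It is also fair to say that the two-level model term is an inference. Section 8.3 names no covariates, and that gap comes before the coding of any one of them. But 7.4 and Table 4 are the only covariate definitions the analyst has, and neither gives weeks a role.

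The classes have a use: they follow the preterm classification in 3.1 and stratify the descriptive tables. That use does not require a binary model term.

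Three stronger readings are tempting.
- A reader might take the loss in variance of weeks as a loss of trial information. It is not: it concerns one covariate, and its effect on the treatment estimate is far smaller.
- A reader might extend the point to the 5-minute Apgar score, of which 7.4 says "It is a quantitative variable, but categorized in the following intervals". Its three bands match Annex 1, and no calculation here supports recoding it.
- A reader might see misclassification in the 28-32 label in 7.4. Inclusion is already below 32 weeks, so no infant is placed wrongly and the label is a clerical matter.

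**Conclusion.** The point holds at minor severity. The plan collects weeks and gives them no analytic role, and no reason is stated for using the split in the models. The coarser coding introduces no confounding and leaves 271 per arm unchanged. The pull towards zero in the Cox model arises because part of a prognostic variable is left out, not because the arms are incomparable.

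The split discards 25-46% of the variance of weeks taken alone, or 14-37% with birthweight in the model. For reintubation this costs roughly 0-2% of the standard error and 0-2 points of power. For weaning time the cost may be larger, but its size rests on an unknown correlation and on the no-censoring assumption. None of these losses can be derived from the documents alone.

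**What to change.** In 7.4, Table 4 and 8.3, state that gestational age enters both the Poisson and the Cox model as a continuous covariate in weeks, as already collected on the Annex 7 form. Name one functional form in advance, for example linear, so that it is not chosen after seeing the data. Keep the under-28 and 28.0-31.6 week classes, as defined in 3.1, for the stratified descriptive tables.

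The cost is a few words in the plan. No new data, form change or extra infants are needed. It should be settled before the data are analysed.
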